	
specimens on an area of normal tissue within the surgical field using the intraoperative NIR camera. The SOC specimens are to be resected upon the initiation of surgery and imaged on a section of normal tissue (i.e., mesentery). Specimen names and fluorescence status will be dictated by the surgeon and documented in the Imaging Workbook by the research coordinator.
 
At the conclusion of SOC resection, the intraoperative NIR camera will be used to investigate the peritoneal cavity further for evidence of residual metastases highlighted by fluorescence. Additional fluorescent specimens will be imaged in situ and then ex situ on an area of normal tissue within the surgical field prior to sending all surgical specimens to pathology for examination. The fluorescence status of each specimen will then be directly correlated to the histopathological outcomes of each specimen. This study design enables the calculation of pegasitacianine sensitivity, specificity, NPV, and PPV. Additionally, Completeness of Cytoreduction (CC) scores can be calculated following SOC resection and adjusted following the resection of additional fluorescent metastases, if warranted.

Endpoints	
Primary Endpoints:
 
 • Detection of disease left behind following SOC resection of peritoneal metastases. Detection of a single additional tumor-containing specimen excised as a result of pegasitacianine fluorescence will be deemed a clinically significant event (CSE) • Alteration to initial Completeness of Cytoreduction scores following imaging with pegasitacianine 
Secondary Endpoints:
 
 • Acceptable safety profiles following pegasitacianine administration • Sensitivity • Specificity • NPV • PPV
Study Drug	
m /k of pegasitacianine
 
prior to surgery

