Statistical Analysis	Proportion of patients for whom an additional metastatic deposit was found and confirmed to be tumor using fluorescence imaging will be calculated by determining the quotient of subjects with a CSE over the total number of patients undergoing surgery who have received >75% of the intended dose of pegasitacianine and have sufficient imaging data. Sensitivity and specificity will be determined at the specimen level using correlated fluorescence observations and pathological outcomes.
Schedule of Events	
Screening (Day -30 to 0)
 
Before the study doctor can administer pegasitacianine, he/she must ensure that it is safe for the patient to be in the study vis-à-vis information that is already known about pegasitacianine. After the patient has agreed to be in the study and signed the informed consent form, the study team will perform the following procedures:
 
 • Record their complete medical history • Perform a complete physical examination

	
• Measure their weight and height and calculate a body mass index (BMI) to estimate body fat tissue• Record vital signs (temperature, heart rate, blood pressure, and breathing rate)• Obtain a blood sample for routine laboratory tests, including a pregnancy test for females who are capable of becoming pregnant• Record medications they have been taking, including prescription, over-the-counter, and herbal medications• Confirm that the patient has met all the study criteria to participate

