9.3 Rate of Clinically Significant Events

Determining the rate of clinically significant events (CSE) detected by pegasitacianine at the subject-level is the primary objective of this study. CSEs will include pegasitacianine detection of

occult disease not otherwise known by the surgeon to exist, the detection of a positive surgical margin, and accurate identification of tumor negative SOC biopsies. A list of CSEs and their definitions is provided below.

- Detection of Occult Disease or Positive Surgical Margins – identification of tumor-containing tissue due to pgsitacianine fluorescence, confirmed via histopathological analysis, that otherwise went undetected during pre-operative imaging (PET, MRI) or by the surgeon during SOC surgery
 - This occurs when a sample that (1) exhibits fluorescence *in situ* and (2) is pathologically-confirmed as a tumor, is obtained by fluorescence during SOC surgery.
- Tumor Negative SOC Biopsies – during SOC surgery, the surgeon will collect tissue specimens that are suspicious for disease. If those samples do not demonstrate pgsitacianine fluorescence and are found to be devoid of tumor pathologically, those specimens would be included as a tumor negative SOC biopsy
 - This occurs when a sample that (1) exhibits no fluorescence *ex situ* and (2) is pathologically-confirmed as normal tissue, is classified as suspicious tissue during SOC surgery.
- Alteration to the Completeness of Cytoreduction (CC) Score – following the completion of the SOC surgery, the surgeon will document a CC score prior to fluorescence imaging using pgsitacianine. If the surgeon finds residual disease using fluorescence imaging that results in the increase of the CC score, this will be considered a CSE

The number and proportion (with corresponding two-sided exact 95% confidence intervals) of subjects with any CSE will be reported.

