2. STUDY OBJECTIVES

2.1 Objectives and Endpoints

The main objective of this study is to investigate whether pegsitarcianine can detect residual disease in the peritoneal cavity following standard of care (SOC) resection of peritoneal metastases using a [REDACTED] mg/kg dose administered [REDACTED] prior to surgery.

Table 1. Objectives and Endpoints

Objectives	Endpoints
Primary Objective	Primary Endpoint

The primary objective of this study is to determine if administration of pegasitacianine (█ mg/kg) results in the detection of metastatic disease left behind following standard of care surgical resection of peritoneal metastases.
	
Rate of detection of disease left behind following SOC resection of peritoneal metastases as measured by rate of Clinically Significant Events (CSEs).

Secondary Objectives	Secondary Endpoints

Demonstrate reliable sensitivity, specificity, negative predictive values (NPPV), and positive predictive values (PPV) of the imaging agent at the level of the individual specimens.
	
Sensitivity, specificity, negative predictive values (NPV), and positive predictive values (PPV).

Demonstrate an acceptable safety profile.	Incidence of TEAEs and SAEs, abnormalities in lab values, vital signs, or ECG results.
Exploratory Objectives	Exploratory Endpoints
Assess the how the normalized SBR value affects the diagnostic accuracy of pegsitacianine in detection of metastatic disease vs. normal tissue.	ROC analysis across various specimen-to-background ratio fluorescence thresholds.
Effect of camera system on diagnostic results.	Diagnostic results across various camera systems.
Assess amount of fluorescence shown in various types of specimens.	Mean fluorescence intensity and Specimen-to-background ratio

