5. ANALYSIS ENDPOINTS

5.1 Efficacy Endpoints

5.1.1 Clinically Significant Event Endpoints

The primary endpoint will include the identification of a clinically significant event (CSE) detected by pegasitacanine. CSEs will include increase in the Completeness of Cytoreduction

score following standard of care surgery, pegasitacianine detection of occult disease not otherwise known by the surgeon to exist, the detection of a positive surgical margin, and accurate identification of tumor negative SOC biopsies. A list of CSEs and their definitions is provided below.

- Detection of Occult Disease or Positive Surgical Margins – identification of tumor-containing tissue due to pegasitacianine fluorescence, confirmed via histopathological analysis, that otherwise went undetected during pre-operative imaging (PET, MRI) or by the surgeon during SOC surgery.
 - This occurs when a sample that (1) exhibits fluorescence *in situ* and (2) is pathologically-confirmed as a tumor, is obtained by fluorescence during SOC surgery.
- Tumor Negative SOC Biopsies – during SOC surgery, the surgeon will collect tissue specimens that are suspicious for disease. If those samples do not demonstrate pegasitacianine fluorescence (e.g. do not exhibit fluorescence *ex situ*) and are found to be devoid of tumor pathologically, those specimens would be included as a tumor negative SOC biopsy.
 - This occurs when a sample that (1) exhibits no fluorescence *ex situ* and (2) is pathologically-confirmed as normal tissue, is classified as suspicious tissue during SOC surgery.
- Alteration to the Completeness of Cytoreduction (CC) Score – following the completion of the SOC surgery, the surgeon will document a CC score prior to fluorescence imaging using pegasitacianine. If the surgeon finds residual disease that results in the increase of the CC score, this will be considered a CSE.

A subject with any CSE will be considered a CSE responder.

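### The any-CSE rate is put forward as the rate of detecting disease left behind, yet one benign, non-fluorescent standard-of-care biopsy is enough to count a subject

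*SAP*

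**What the plan says.** SAP Table 1 (section 2.1) gives one primary endpoint: "Rate of detection of disease left behind following SOC resection of peritoneal metastases as measured by rate of Clinically Significant Events (CSEs". The primary objective, in both documents, asks only about metastatic disease left behind.

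SAP 5.1.1 lists the CSE types: occult disease or a positive margin, a tumor-negative SOC biopsy, and a change in the Completeness of Cytoreduction (CC) score. The tumor-negative type needs a specimen that shows no fluorescence ex situ and "is pathologically-confirmed as normal tissue, is classified as suspicious tissue during SOC surgery". The section closes with the responder rule: "A subject with any CSE will be considered a CSE responder".

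Protocol 9.3 has the same list. Suspicious SOC specimens that do not fluoresce and are "found to be devoid of tumor pathologically, those specimens would be included as a tumor negative SOC biopsy" count as CSEs, and the number and proportion "of subjects with any CSE will be reported" with an exact 95% interval.

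The Protocol Summary, under Statistical Analysis, describes a different quantity: "Proportion of patients for whom an additional metastatic deposit was found and confirmed to be tumor using fluorescence imaging". The same entry takes its numerator to be all subjects with a CSE, and its denominator to be operated patients given over three quarters of the planned dose whose imaging data suffice.

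SAP 7.10.1.1 summarizes CSE responders and also each CSE type, by Group, with Clopper-Pearson intervals.

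**The concern.** The label and the count do not match. A tumor-negative SOC biopsy is tissue that was already removed, did not fluoresce and contained no tumor. It is a specimen-level true negative, so it bears on specificity and NPV, where it is already counted. It says nothing about disease remaining after resection.

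This event type also moves in the wrong direction for the stated objective. The less the agent fluoresces, the more benign suspicious specimens qualify, and an agent that never fluoresced would reach the maximum.

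Both sample size sections say the study is meant to inform power calculations for later trials. A headline rate that mixes residual-disease detection with how often surgeons remove benign tissue could mis-size a trial of residual-disease detection.

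**Working it through.** **The texts side by side**

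| Place | What the CSE rate is or counts |
|---|---|
| Protocol Summary, Statistical Analysis | Patients with an additional, tumor-confirmed deposit found by fluorescence |
| Protocol 9.3 | Subjects with any CSE, including a tumor-negative SOC biopsy |
| SAP Table 1 | Rate of detection of disease left behind |
| SAP 5.1.1 | Any CSE, including a tumor-negative SOC biopsy |

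A subject whose only event is a benign, non-fluorescent, surgeon-suspicious SOC specimen is counted under rows 2 and 4 and does not fit rows 1 and 3. The SAP's precedence clause (section 1) does not settle this, because rows 3 and 4 are both in the SAP.

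**Possible size.** The plan states no CSE rate, target or precision, so there is no figure to reproduce. What follows is illustration.

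Inputs:
- k, suspicious SOC specimens per subject: the ceiling of 10 is in Protocol 6.3; the low value of 3 is assumed.
- b, benign share of those specimens: not given; 1% to 10% assumed.
- s, specificity: no peritoneal figure is given; 57% and 75% are borrowed from the head-and-neck and breast results in Protocol 1.2.
- ρ, within-subject correlation: not given; 0 to 0.2 assumed.
- r, true detection rate: not given; 30% assumed.
- Residual-disease detection and tumor-negative biopsies are taken as independent, and CC-score changes are left out.

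Formulas: p = b × s is the chance that a suspicious specimen is benign and non-fluorescent. The chance q that a subject has at least one is 1 − (1 − p)^k when ρ = 0. Otherwise q = 1 − P(X = 0), with X beta-binomial(k, p(1−ρ)/ρ, (1−p)(1−ρ)/ρ). The any-CSE rate is r + (1 − r)q.

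| k | b | s | ρ | p | q | Any-CSE rate when r = 30% |
|---|---|---|---|---|---|---|
| 3 | 1% | 57% | 0.2 | 0.0057 | 0.014 | 31% |
| 5 | 10% | 75% | 0.2 | 0.075 | 0.239 | 47% |
| 10 | 10% | 75% | 0.2 | 0.075 | 0.339 | 54% |
| 10 | 10% | 75% | 0 | 0.075 | 0.541 | 68% |

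First row: the beta parameters are 0.0228 and 3.9772, so P(X = 0) = (3.9772/4)(4.9772/5)(5.9772/6) = 0.986, and 0.30 + 0.70 × 0.014 = 0.31. Last row: 1 − 0.925^10 = 0.541, and 0.30 + 0.70 × 0.541 = 0.68.

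Without independence, the rate lies between max(r, q) and r + q: 30% to 31% for the first row and 54% to 84% for the last.

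For scale, 18/60 = 30% has an exact 95% interval of 18.8% to 43.2%. The first row is well inside it and the last three rows are above it. Sixty is planned enrollment; the efficacy population may be smaller.

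**An agent that never fluoresces** (s = 1, r = 0): the any-CSE rate equals q. It is 2.5% at k = 3, b = 1%, ρ = 0.2, and 1 − 0.9^10 = 65% at k = 10, b = 10%, ρ = 0. The correct detection rate is 0%.

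**The case against.** The best defence is that nothing is hidden or lost. Both documents list the tumor-negative type openly and in matching terms. SAP 7.10.1.1 gives each CSE type its own exact interval and a per-patient listing, and SAP 7.10.2.1 lists fluorescence and pathology for every specimen. A later power calculation can use the occult-disease row directly. A never-fluorescing agent would show zero in that row and zero sensitivity in the same report. All of this stands, and it limits the harm. It does not settle the point, because no passage says that the occult-disease row answers the primary objective, and SAP Table 1 points to the overall CSE rate.

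It can also be argued that sparing benign tissue is useful in itself. Perhaps so, but that is a different quantity from the one the label names.

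Some stronger readings go too far:
- A reader might infer that a study conclusion is exposed to error. The study is not powered for hypothesis testing, and Protocol 3.1 opens Group 2 on sensitivity and specificity.
- A reader might take the primary endpoint entry in the Protocol Summary to exclude every other kind of CSE. It states only a sufficient condition: "Detection of a single additional tumor-containing specimen excised as a result of pegasitacianine fluorescence will be deemed a clinically significant event (CSE". The exclusive reading rests on the Statistical Analysis entry.
- A reader might suppose that the five planned normal specimens create responders. They do not; the specimen must have been classified as suspicious.
- A reader might conclude that the tumor-negative type must leave the composite. The inconsistency does not require that; correct labelling is enough.

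**Conclusion.** The point holds as an inconsistency about which rate answers the primary objective. Read literally, the plan reports a primary rate that does not measure its label, and the Protocol Summary and Protocol 9.3 count different numerators under one term. That conclusion rests on the text alone.

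It is tempting to add that the inflation is large. The documents do not support this. They give no benign fraction, expected specimen count, correlation, expected detection rate or peritoneal specificity. Under the assumptions above, a true 30% could read from about 31%, which is trivial, to about 68%, which would dominate the result. The finding should be fixed, but no data are lost and no test or decision rule is affected.

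**What to change.** Before database lock, through the protocol amendment that SAP 7.1 calls for when a change may affect the primary conclusions:

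1. In the Protocol Summary (Statistical Analysis), Protocol 9.3, SAP Table 1, SAP 5.1.1 and SAP 7.10.1.1, name the planned occult-disease/positive-margin row as the primary estimate of residual-disease detection. Keep its conditions: fluorescence in situ, tumor confirmed by pathology, and otherwise undetected by pre-operative imaging or by the surgeon during SOC surgery. In the same change, correct the sub-bullet in Protocol 9.3 and SAP 5.1.1 that places fluorescence-guided collection during SOC surgery. Protocol 3.1 and 6.3 place it after SOC resection, and 6.3 bars camera examination of the cavity before then. Read literally, the sub-bullet would exclude the post-resection specimens and so would decide the primary numerator.
2. Keep the any-CSE rate as a supportive composite, labelled as including benign, non-fluorescent biopsies, and do not present it as the rate of detection of disease left behind. Continue to report the tumor-negative SOC biopsy row separately.

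The cost is small: no new data and no new table. The headline rate will be lower. The change also comes late in an open-label study (the SAP is version 3, January 2023), so it could look data-driven. Date it, record what was known of the data at that time, and report both rates.

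A separate minor point: the Protocol Summary lists CC-score alteration as its own primary endpoint, while SAP Table 1 has a single primary endpoint and SAP 5.1.1 makes it a CSE type. The two documents should agree.

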5.1.2 Diagnostic Imaging Endpoints

Diagnostic performance of pegasitacianine will be assessed by calculating sensitivity, specificity, NPV and PPV of pegasitacianine in detecting tumor containing tissue. The *ex situ* fluorescence status (any fluorescence vs. no fluorescence) of collected SOC and pegasitacianine guided specimens, as well as lymph nodes, will be compared to histological analyses of the collected specimens. Sensitivity and specificity for detecting tumor-containing tissue versus normal tissue

will be evaluated using tissue specimen fluorescence and the corresponding pathological outcomes.

True/false negative/positive definitions are as follows:

- False positive is defined as fluorescence was observed on the sample but the sample was not found to have tumor via pathology.
- False negative is defined as no fluorescence was observed on the sample but the sample was found to have tumor via pathology.
- True positive is defined as fluorescence was observed on the sample and the sample was found to have tumor via pathology
- True negative is defined as no fluorescence was observed on the sample and the sample was found not to have tumor via pathology.

Pegsitacianine sensitivity and PPV will be calculated using the following equations:

$$\text{Sensitivity} = \frac{\# \text{ of True Positive Specimens}}{\# \text{ of True Positive Specimens} + \# \text{ of False Negative Specimens}}$$

$$\text{PPV} = \frac{\# \text{ of True Positive Specimens}}{\# \text{ of True Positive Specimens} + \# \text{ of False Positive Specimens}}$$

Specificity values and negative predictive values (NPV) calculated by the equation below:

$$\text{Specificity} = \frac{\# \text{ of True Negative Specimens}}{\# \text{ of True Negative Specimens} + \# \text{ of False Positive Specimens}}$$

$$\text{NPV} = \frac{\# \text{ of True Negative Specimens}}{\# \text{ of True Negative Specimens} + \# \text{ of False Negative Specimens}}$$

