3. STUDY PLAN

3.1 Overall Design

This Phase 2 study will be a an interventional, open-label, single arm trial where each patient is his/her own “intrapatient” control usin two Grou s. All patients will receive a single mg/kg dose of pegasitacianine prior to standard of care surgery.

Patients enrolled in Group 1 of the study will have a biopsy confirmed diagnosis of non-mucinous peritoneal carcinomatosis, defined as less than, or equal to 50% mucin in the sample, with a suspected Peritoneal Carcinomatosis Index (PCI) greater than or equal to . Group 2 of the study will include patients with a suspected PCI greater than or equal to and a biopsy confirmed diagnosis of mucinous peritoneal carcinomatosis, defined as > 50% mucin in the sample. A total of approximately 60 patients will be enrolled across both Groups. Enrollment will be open first to Group 1 with the opportunity to open Group 2 for enrollment following the demonstration of satisfactory pegasitacianine sensitivity and specificity values of 70% or greater in Group 1.

In both Groups 1 and 2, the surgeon will perform their SOC resection of visible metastases and image each resected specimen, and normal specimens on an area of normal tissue using the intraoperative NIR camera; no investigative NIR imaging of the peritoneal cavity will be performed at this time. The SOC specimens are to be resected upon the initiation of surgery and imaged on a section of normal tissue (i.e., mesentery). Specimen names and fluorescence status will be dictated by the surgeon and documented in the Imaging Workbook by the Clinical Research Coordinator.

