6.3 Surgery and Follow-up Visits (Group 1 and 2)

Procedures at the time of cytoreductive surgery

The following procedures will be performed on the day of surgery:

- Record the patient's vital signs (only if they were abnormal at dosing)

- Obtain blood for routine laboratory tests
- Record all medications being taken, including prescription, over-the-counter, and herbal medications
- Discuss with the patient any new or unexpected changes they are feeling
- Record any AEs

Once the patient is under anesthesia, some procedures will occur that would not normally be part of surgery if the patient were not in this study. The SOC surgical procedures will be allowed to continue with the addition of the steps listed below.

- During SOC resection, the surgeon will select up to 15 (10 suspected tumor and 5 normal) specimens that will be imaged using the intraoperative camera on a section of normal tissue following excision (*Note: NIR camera should not be used to examine the peritoneal cavity at this time*)
 - A total of up to 15 specimens are to be imaged: 5 representative normal pieces of tissue and 10 individual suspected tumor specimens
 - The SOC specimens are to be resected upon the initiation of surgery and imaged on a section of normal tissue (i.e., mesentery) immediately following the collection of all SOC samples
 - The width of the camera's field of view is to be confined to a distance of 10 cm. A surgical ruler is to be placed in frame to control the width of the field of view
 - Note: while there are no specimen size stipulations provided in this protocol, the samples must be able to be imaged within the 10 cm wide imaging window.
 - For samples with multiple nodules, individual nodules should be dissected away from the bulk sample and imaged individually as single specimens.
 - Representative normal sections of tissue should be imaged in an analogous manner
- Samples will be imaged using the NIR camera and fluorescence status and specimen name will be dictated by the surgeon for documentation by the clinical research coordinator in the provided Imaging Workbook
- Once the SOC resection is complete, the surgeon will dictate their completeness of cytoreduction score to the clinical research coordinator for documentation prior to examining the peritoneal cavity with the intraoperative NIR camera in search of additional fluorescent metastatic disease that was missed during SOC

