 - The peritoneal cavity will be evaluated using a manner similar to that used for

the calculation of the Peritoneal Carcinomatosis Index. Specifically, the peritoneal cavity will be examined in a methodical manner using the 13 described regions used for calculating the PCI score

- If additional fluorescent areas are to be collected, an image of the additional fluorescent lesion(s) is to be captured prior to excision from the patient
 - The camera should be held 15 cm away from the area of tissue to be excised. The camera's distance can be measured using an available surgical ruler
- Additional fluorescent lesions will then be removed and imaged on a section of normal tissue in a manner analogous to the SOC specimens with the surgeon dictating fluorescence status and specimen name to the clinical research coordinator for documentation
 - The width of the camera's field of view is to be confined to a distance of 10 cm. A surgical ruler is to be placed in frame to control the width of the field of view

Day 10 (± 5 days) or Day of Discharge (Whichever event occurs first)

- Record the patient's vital signs
- Perform 12-lead ECG to monitor heart activity
- Perform a physical examination
- Obtain blood samples for routine laboratory tests
- Record all medications being taken, including prescription, over-the-counter, and herbal medications
- Discuss any new or unexpected changes they are feeling.
- Record any AEs

Day 28 (± 5 days) after dosing

- Obtain blood samples for routine laboratory tests, including a pregnancy test for females who are capable of becoming pregnant
- Record all medications they are taking, including prescription, over-the-counter, and herbal medications
- Discuss new or unexpected changes they are feeling
- Record the patient's vital signs

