9.4 Imaging Analysis

Diagnostic performance of pgsitacianine will be assessed at the level of the specimen by calculating the *ex situ* sensitivity, specificity, PPV, and NPV of pgsitacianine in detecting tumor containing tissue. The *ex situ* fluorescence status of collected SOC and pgsitacianine guided specimens will be compared to the histological analyses of the collected specimens (which is used to determine each sample's status as true/false positive/negative). For determining these operating characteristics, consider the following definitions:

- False positive is defined as “fluorescence was observed on the specimen but the specimen was not found to have tumor via histological analysis”.
- False negative is defined as “no fluorescence was observed on the specimen but the specimen was found to have tumor via histological analysis”.

- True positive is defined as “fluorescence was observed on the specimen and the specimen was found to have tumor via histological analysis”.
- True negative is defined as “no fluorescence was observed on the specimen and the specimen was found not to have tumor via histological analysis”.

The number of specimens in each category (each combination of true/false positive/negative), along with the true/false positive/negative rates (and corresponding exact two-sided 95% confidence intervals) will be reported. These rates will be used to determine pegsitacianine’s tumor detection sensitivity, specificity, PPV, and NPV using the following equations:

$$\text{Sensitivity} = \frac{\text{\# of True Positive Specimens}}{\text{\# of True Positive + False Negative Specimens}}$$

$$\text{Specificity} = \frac{\text{\# of True Negative Specimens}}{\text{\# of True Negative Specimens + \# of False Positive Specimens}}$$

$$\text{PPV} = \frac{\text{\# of True Positive Specimens}}{\text{\# of True Positive + False Positive Specimens}}$$

$$\text{NPV} = \frac{\text{\# of True Negative Specimens}}{\text{\# of Tumor Negative + False Negative Specimens}}$$

These rates will be reported along with exact two-sided 95% confidence intervals.

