7.10.2 Secondary Analyses

7.10.2.1 Analysis of Diagnostic Imaging

The positive predictive value, negative predictive value, sensitivity, and specificity (biopsy level) will be calculated and summarized for each Group. The summary will include the true/false negatives/positive rate and number of specimens. Two-sided 95% confidence intervals will be calculated for each rate via Clopper-Pearson method.

A listing by subject and specimen showing the fluorescence status, pathology result, specimen type (SOC vs. fluorescence), suspicious vs. normal, fluorescence in *in situ* and *ex situ*, and fluorescence measures (MFI, SBR or TBR) will be provided.

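### Pooled PPV and NPV reflect how specimens are sampled as well as how the agent performs, and the SAP neither separates the two nor says so

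*SAP*

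**What the plan says.** SAP 5.1.2 sets out the four accuracy measures together: "Diagnostic performance of pegasitacianine will be assessed by calculating sensitivity, specificity, NPV and PPV of pegasitacianine in detecting tumor containing tissue".

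Protocol 6.3 sets a sampling target for the SOC phase: "A total of up to 15 specimens are to be imaged: 5 representative normal pieces of tissue and 10 individual suspected tumor specimens". The choice of specimens is the surgeon's. Protocol 3.1 describes the same step differently. There the surgeon is to "image each resected specimen, and normal specimens on an area of normal tissue using the intraoperative NIR camera", with no 10-and-5 target, and SAP 3.1 follows that description. These sections need to be reconciled.

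After SOC resection a second kind of specimen is collected because it fluoresces: "Additional fluorescent lesions will then be removed and imaged on a section of normal tissue in a manner analogous to the SOC specimens". No number or cap is given.

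All of these enter one table. Protocol 9.4 compares the ex situ "fluorescence status of collected SOC and pgsitacianine guided specimens will be compared to the histological analyses of the collected specimens". SAP 5.1.2 widens the set to the ex situ status "of collected SOC and pegasitacianine guided specimens, as well as lymph nodes, will be compared to histological analyses of the collected specimens". Pathology, not the surgeon's label, decides whether a specimen counts as tumour. PPV and NPV are then plain ratios of counts. SAP 7.10.2.1 reports them this way: "The positive predictive value, negative predictive value, sensitivity, and specificity (biopsy level) will be calculated and summarized for each Group". Specimen type (SOC or fluorescence-guided) and the suspicious or normal label appear only in a listing.

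**The concern.** PPV and NPV can be read straight from counts only if the specimens occur in the mix to which the values will be applied. Here part of the mix is a design choice. Tissue chosen because it looks normal adds mainly true negatives, with some false positives. Tissue chosen because it fluoresces adds almost only true and false positives.

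Two uses of the results are at stake. The secondary objective is to show reliable predictive values for individual specimens, and a surgeon would read NPV as the chance that a suspicious lesion without fluorescence is benign. A pooled NPV drawn largely from tissue nobody suspected does not answer that. Protocol 9.1 and SAP 4 also say the trial is meant to inform power calculations for later studies. A pooled NPV would mislead in any study with a different share of normal tissue.

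No planned analysis deals with this. The mixed-model ROC curve and cluster bootstrap (SAP 7.10.3.3) address within-subject correlation. The optional covariate work (SAP 7.10.3.5) covers sensitivity and specificity only.

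**Working it through.** The documents state no PPV, NPV or tumour share, so there is no figure to reproduce.

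**Inputs.** From Protocol 6.3: 10 suspected and 5 normal SOC specimens per patient, taken at the ceiling. Assumed: sensitivity (Se) and specificity (Sp) both 0.70, borrowed from the threshold for opening Group 2 and not an expected result; the same Sp for normal and for benign suspicious tissue; all five normals tumour-free; a share q of the ten suspected specimens confirmed as tumour.

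**Formulas.** PPV = TP/(TP+FP); NPV = TN/(TN+FN).

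**Step 1, effect of the five normals at q = 0.80** (8 tumour, 2 benign suspicious, 5 normal).
- In both cases TP = 8 × 0.70 = 5.6 and FN = 8 × 0.30 = 2.4.
- Normals pooled: FP = 7 × 0.30 = 2.1 and TN = 7 × 0.70 = 4.9. PPV = 5.6/7.7 = 0.727; NPV = 4.9/7.3 = 0.671.
- Normals left out: FP = 2 × 0.30 = 0.6 and TN = 2 × 0.70 = 1.4. PPV = 5.6/6.2 = 0.903; NPV = 1.4/3.8 = 0.368.

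The agent and the suspected specimens are the same, yet PPV moves by 18 points and NPV by 30. Of the 4.9 expected true negatives, 5 × 0.70 = 3.5 (71%) come from the chosen normals.

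**Step 2, range over q**, by the same formulas:

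| q | PPV / NPV, normals pooled | PPV / NPV, normals left out |
|---|---|---|
| 0.9 | 6.3/8.1 = 0.778; 4.2/6.9 = 0.609 | 6.3/6.6 = 0.955; 0.7/3.4 = 0.206 |
| 0.8 | 0.727; 0.671 | 0.903; 0.368 |
| 0.5 | 3.5/6.5 = 0.538; 7.0/8.5 = 0.824 | 3.5/5.0 = 0.700; 3.5/5.0 = 0.700 |

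**Step 3, other assumed accuracy.** Take Se 0.90, Sp 0.70 and 9% of the suspected specimens benign.
- Pooled (9.1 tumour, 5.9 not): PPV = 8.19/(8.19+1.77) = 0.82; NPV = 4.13/(4.13+0.91) = 0.82.
- Normals left out (9.1 and 0.9): PPV = 8.19/(8.19+0.27) = 0.97; NPV = 0.63/(0.63+0.91) = 0.41.

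The shifts are about 15 points for PPV and 41 for NPV.

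**Step 4, guided specimens.** Add to the pooled case of step 1 five guided specimens, assumed all fluorescent ex situ and half confirmed as tumour. TP becomes 5.6 + 2.5 = 8.1 and FP becomes 2.1 + 2.5 = 4.6.
- PPV = 8.1/12.7 = 0.638, down from 0.727. NPV stays at 0.671.
- Apparent sensitivity = 8.1/10.5 = 0.771 and apparent specificity = 4.9/9.5 = 0.516, against 0.70 for each.

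Guided specimens therefore distort sensitivity and specificity too.

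**Step 5, does the agent still count?** At a tumour share of 10/15, Se = Sp = 0.50 gives PPV 0.667 and NPV 0.333, and Se = Sp = 0.90 gives 0.947 and 0.818. It does.

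**The case against.** A reader might infer that the protocol fixes the mix at 10 to 5, so that PPV and NPV measure the quota rather than the agent and have no clinical meaning. The documents do not support that. The counts are ceilings, and the ten are only suspected. With the target fully met, q from 1.0 to 0.5 moves the tumour share from 10/15 to 5/15. Guided specimens and lymph nodes come on top without a stated number. Step 5 shows that accuracy still moves both values widely.

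A reader might also be tempted to measure the effect against a reversed mix of 5 tumour to 10 normal. At Se 0.90 and Sp 0.70, PPV is then 0.60 against 0.86 at 10 to 5. No such mix appears in the documents. The relevant contrast is with and without the five normals, at one confirmation rate.

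It can fairly be said that the specimen listing already carries what a split needs. Non-fluorescent, tumour-free suspicious SOC tissue is also counted as a type of clinically significant event (CSE) (SAP 5.1.1). The listing makes the fix cheap but does not commit anyone to the analysis. The event count records true negatives at patient level without the matching false negatives, so it yields no NPV.

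The point about stakes stands. These are descriptive secondary endpoints in a study not powered for testing. Neither the primary CSE rate nor the Protocol 3.1 criterion for opening Group 2 uses PPV or NPV.

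**Conclusion.** The concern holds in a limited form. As planned, PPV and NPV mix the agent's performance with the sampling scheme, and the SAP offers no split, adjustment or caveat. The mix is shaped by the protocol, not fixed by it, and an uncontrolled mix makes the pooled values harder to interpret, not easier.

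Under the two main illustrations, the chosen normals alone shift PPV by about 15 to 18 points and NPV by about 30 to 41. At q = 0.5 the shifts are smaller (16 and 12 points). All of these rest on assumed accuracy, an assumed confirmation rate, fully used ceilings and one specificity for both kinds of tumour-free tissue. The direction rests on less: adding tumour-free tissue to the suspected specimens at the same accuracy lowers PPV and raises NPV. This is worth correcting before database lock, but it does not threaten the primary result.

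**What to change.** In SAP 5.1.2 and 7.10.2.1:
- Leave the representative normal specimens out of PPV and NPV, and keep them for specificity.
- Report PPV and NPV among surgeon-suspicious SOC specimens.
- Report PPV separately for post-SOC guided specimens. No NPV can be estimated there, because non-fluorescent tissue in the cavity is not sampled. A guided specimen that happens to be negative ex situ does not stand in for it.
- Label any pooled PPV or NPV, including one with lymph nodes, as specific to this sampling scheme.
- If PPV and NPV are also shown over a range of tumour shares, derive them from sensitivity and specificity in SOC specimens only, for the reason in step 4.

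The needed flags are already planned for the SAP 7.10.2.1 listing, so no new data are required. The price is smaller denominators and wider intervals. In the step 1 example the expected NPV denominator falls from 7.3 to 3.8 specimens per patient, and the PPV denominator from 7.7 to 6.2. NPV will probably be lower and PPV higher.
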